## Mapping Biopsy Protocols

After the pre-HIFU imaging protocol for tumor mapping, all patients will undergo a transrectal ultrasound-guided targeted mapping biopsy. The biopsy will include a standard sextant template plus MR/US-fusion targeted biopsy of any lesions with PI-RADS scores ≥3 on hrMRI or F18-PSMA PET positivity. These areas will be targeted using the UroNav targeting software platform. We use the UroNav platform for performing MR-PET-US fusion biopsies. It is an FDA approved, commercially available platform. Uronav received 510(k) clearance from the FDA and it is a commercially available platform, link to document:

https://www.accessdata.fda.gov/cdrh docs/pdf15/K153073.pdf. As an exploratory analysis, remnant formalin-fixed paraffin embedded tumor tissue will be requested for RNAseq transcriptome analysis of lesions that are positive on mapping biopsy.

## Eligibility for HIFU

If subjects are found to have unilateral high grade disease (i.e. Gleason grade 4 or 5), they will be considered as a candidate for hemigland or focal HIFU therapy. Clinician judgment may be exercised in determining eligibility for HIFU, since established criteria based on volume and extent of disease do not exist. If patients have high grade disease in both lobes, they will not be eligible for HIFU therapy on this trial. Their data will be used to assess the primary endpoint but they will not be considered for secondary endpoints.

## HIFU Therapy and Follow Up Schedule

Patients who are eligible for HIFU will receive hemigland or focal HIFU per standard-of-care. All subjects will receive repeat mpMRI and MR/US-guided biopsy of all positive sites + systematic 12-core prostate biopsy at 6 months (or as clinically indicated). As an exploratory analysis, remnant formalin-fixed paraffin embedded tumor tissue will be requested for RNAseg transcriptome analysis of lesions that are positive on biopsy.

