# **STUDY SUMMARY**

Title	High-Resolution, 18F-PSMA PET-MRI for Mapping Prostate Cancer in Patients Considering Focal High-Intensity Focused Ultrasound (HIFU) Therapy or Radical Prostatectomy
Short Title	High resolution PET-MRI before prostate cancer HIFU or radical prostatectomy
Protocol Number	Pro00000832
Phase	Two parts: Phase II and Pilot
Methodology	Single arm, paired imaging (Phase II)
Study Duration	3 years
Study Center(s)	Cedars Sinai Medical Center
Objectives	Phase II Study (HIFU): Primary Endpoint: Number of additional biopsy-proven cancers that novel imaging modalities of hrMRI and/or F18-PSMA PET would detect when compared to reference standard imaging of mpMRI in patients undergoing HIFU procedure. Secondary Endpoint: Negative biopsy rate of standard 12-core biopsy 6 months following HIFU therapy.  Phase II Study (Radical Prostatectomy(RP)): Primary Endpoint: To determine the sensitivity in detection of prostatic carcinoma of novel imaging modalities of hrMRI and /or F18-PSMA PET compared to reference standard mpMRI in patients scheduled to undergo radical prostatectomy. Secondary Endpoint: Specificity of hrMRI, F18PSMA PET and mpMRI for detecting all tumors and metastasis at 6 months follow up.
Number of Subjects	30 Study Subjects (Phase II HIFU), 31 Study Subjects (Phase II RP)

Diagnosis and Main Inclusion Criteria	
 
Diagnosis for Pilot trial: Any patient scheduled to undergo radical prostatectomy Diagnosis: Clinically localized, unilateral, high-grade prostate cancer OR at high risk for having unrecognized high grade Prostate Cancer Inclusion Criteria:         
 
Biopsy consisting of ≥ 10 tissue cores sampled
 
PSA ≤20 ng/mL
 
cT1-cT2c
 
Either overall Gleason score ≥ 7 with Gleason grade 4 or 5 component localized to one lobe (i.e. right or left) OR overall Gleason score 6 with ≥ half of systematic biopsy cores positive and ≥ 50% of core involvement in at least one core
 
Patients considering focal HIFU therapy
 
Patients considering radical prostatectomy
 
 
 
		
Study Imaging	F18-PSMA PET-MRI in combination with multiparametric prostate MRI using high resolution DWI		
Control Imaging	Standard multiparametric prostate MRI		
Reference standard	MRI-targeted prostate biopsies will serve as the reference standard and all lesions seen on any MRI protocol will be biopsied. In the pilot trial, the prostatectomy pathology will serve as the reference standard.		

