We herein propose a prospective trial to evaluate the effectiveness of F18-PSMA PET-hrMRI versus standard mpMRI at identifying prostate cancer targets for HIFU therapy. Patients with clinically localized, unilateral high grade prostate cancer (Gleason score 7-10 prostate cancer localized to one lobe on prior biopsies) OR at high risk for having unrecognized high grade prostate cancer (overall Gleason score 6 with ≥ half of systematic biopsy cores positive and ≥ 50% of core involvement in at least one core), interested in HIFU would receive both a standard mpMRI and F18-PSMA PET-hrMRI. They would then undergo a mapping biopsy using a standard sextant template plus MRI/US-fusion targeted biopsy of any suspicious lesion on mpMRI or PET-hrMRI. The primary endpoint would assess the number of biopsy-proven cancers that mpMRI would have missed compared with PET-hrMRI. Following our tumor mapping study, patients with high grade disease (i.e. Gleason grade 4 or 5) in one lobe undergo hemigland or focal HIFU of that lobe. At 6 months, patients would undergo repeat prostate biopsy to assess the negative biopsy rate in the treated region and absence of Gleason grade 4 or 5 in the untreated region as secondary endpoints.

Tumors invisible on MRI tend to be small, low-grade tumors that do not require treatment. However, it may be important to identify these tumors for future surveillance. An important limitation of this phase II study is that it will not be able to define the sensitive of imaging for these low-grade tumors. Therefore, a pilot study is included in which patients scheduled to undergo radical prostatectomy will have a preoperative PET-hrMRI. The prostatectomy pathology will be the reference standard. Since the true location of all tumors will be known, both the sensitivity and specificity of PSMA-PET MRI can be determined

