#### 3.0 STUDY DESIGN:

#### 3.1 Overview

This prospective trial will evaluate the effectiveness of F18-PSMA PET-hrMRI versus standard mpMRI at identifying prostate cancer targets for HIFU therapy. Patients with clinically localized, Gleason score 7-10 prostate cancer localized to one lobe on prior biopsies or overall Gleason score 6 with ≥ half of systematic biopsy cores positive and ≥ 50% of core involvement in at least one core, interested in HIFU would receive both a standard mpMRI and F18-PSMA PET-hrMRI. They would then undergo a mapping biopsy using a standard sextant template plus MR/US-fusion targeted biopsy of any lesions with PI-RADS scores ≥3 on hrMRI or 18F-PSMA PET positivity. The primary endpoint of the Phase II study would assess the number of biopsy-proven cancers that mpMRI would have missed compared with hrMRI and/or F18-PSMA PET. Following our tumor mapping study, patients with high grade disease (i.e. Gleason grade 4 or 5) in one lobe undergo hemigland or focal HIFU of that lobe. At 6 months, patients would undergo repeat mpMRI and prostate biopsy (MR/US-fusion biopsy plus standard sextant biopsy) to assess the negative biopsy rate in the treated region and absence of Gleason grade 4 or 5 in the untreated region which will be the secondary endpoint of the Phase II study.

As the gold standard for evaluation of sensitivity and specificity of any imaging test is the pathologic analysis of the whole prostatic gland obtained at prostatectomy (as the biopsy is subject to error sampling), a concurrent pilot study will enroll patients scheduled to undergo prostatectomy with the primary endpoint to define sensitivity of PET-hrMRI versus mpMRI compared against the prostatectomy pathology and with the secondary endpoint define specificity of hrMRI, F18-PSMA PET and mpMRI for detecting all tumors and metastasis at 6 months follow up.

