## 3.3 Study endpoints

Primary Endpoint (HIFU): Number of additional biopsy-proven cancers that novel imaging modalities of hrMRI and/or F18-PSMA PET would detect when compared to reference standard imaging of mpMRI in patients undergoing HIFU procedure.

Secondary Endpoint (HIFU): Negative biopsy rate on standard 12-core biopsy 6 months following HIFU therapy.

**Primary Endpoint (Prostatectomy):** To determine the sensitivity in detection of prostatic carcinoma of novel imaging modalities of hrMRI and/or F18-PSMA PET compared to reference standard mpMRI in patients scheduled to undergo radical prostatectomy.

Secondary Endpoint (Prostatectomy): Specificity of hrMRI, F18-PSMA PET and mpMRI for detecting all tumors and metastasis at 6 months follow up.

**Exploratory Endpoint:** RNAseq transcriptome analysis of lesions that are positive on mapping biopsy. Sensitivity and specificity of PET-hrMRI for detecting all tumors detected on prostatectomy pathology.

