## 3.4 Study Procedures

#### **3.4.1** Screening/Baseline Procedures

Subjects will be identified by study investigators within the academic urology practice at Cedars-Sinai Medical Center during routine clinical practice. All study assessments for eligibility are performed as part of standard of care. Once a patient has been diagnosed, expressed interest in HIFU, and recommended study participation, they will be presented with the Informed Consent Form, including a description of the study purpose, risks, benefits and possible alternatives. The prospective participant will be given sufficient time to consider participation in the research. Patients will be asked to sign the study consent form after receiving a complete explanation of the study.

This study will enroll patients with clinically localized, Gleason score 7-10 prostate cancer

localized to one lobe on prior biopsies or overall Gleason score 6 with  $\geq$  half of systematic biopsy cores positive and  $\geq$  50% of core involvement in at least one core, interested in HIFU as primary treatment. Patients with low Gleason grade cancer (e.g. Gleason grade 3) on the contralateral lobe are allowed since the standard-of-care for such low grade disease is observation. Patients with very low risk disease and low-volume, low-risk disease are excluded since their preferred management is active surveillance. Patients will present with newly diagnosed disease or after a period of active surveillance. If there is suggestion of extracapsular disease or seminal vesicle involvement on MRI, these patients will be excluded. Metastatic workup with cross sectional imaging and/or bone scan will not be mandatory, since they are not indicated for low- and intermediate-risk prostate cancers according to AUA and NCCN guidelines.

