#### 6.0 STATISTICAL ANALYSIS

# 6.1 HIFU Phase II Study

Our preliminary data suggests that up to 60% of tumors invisible to standard mpMRI are detected on hrMRI in an active surveillance population. It is unclear how many additional lesions will be identified on PSMA PET-MRI. Since all areas of concern will be biopsied and only biopsy-proven tumors will be treated with HIFU, the morbidity of the surgical intervention is minimized and its potential to achieve cure is maximized.

Power Assessment: The main hypothesis to be tested is whether the sensitivity of PSMA PET-hrMRI is greater than mpMRI alone in 20% considering the prostate divided in 6 sections for each patient. The power is evaluated using 1000 simulations based on the McNemar's type test proposed by Yang et al. (17,2010). Data is generated based on four correlations: r1: between lesions evaluated by PSMA PET-hrMRI for the same patient, r2: between lesions evaluated by mpMRI for the same patient, r3: between evaluations PSMA PET-hrMRI and mpMRI for the same lesion and r4: between evaluations PSMA PET-hrMRI and mpMRI for the different lesions at the same patient. Based on preliminary data, we estimated mpMRI sensitivity of 42%, (r1, r2, r3, r4) = (-0.249, -0.119, 0.714, -0.172) using Spearman correlation, average number of lesions of 2.5 per patient and prevalence of patients with at least one positive biopsy section equal to 82%. The results are presented in Table 1.

**Table 1.** Power for McNemar test proposed by Yang et al. (2010) to detect a difference of 20% between sensitivities of the combination (PET-hrMRI or mpMRI) and mpMRI

Total Sample # Patients with at least one positive biopsy
Size section Power

20	16	70.2
25	21	81.5
30	25	88.9
35	29	93.1
40	33	95.5

The minimum sample size to reach at least 85% of power is 30 patients with complete imaging data. Patients with incomplete imaging data will be replaced.

Statistical Analysis: Sensitivities will be compared using McNemar's type test proposed by Yang et al. (17,2010). for cluster matched binary data. In addition, the 95% confidence interval for difference between sensitivities will be calculated as proposed by Yang et al. (18,2012).

Secondary Endpoints: Negative biopsy rate within treatment zones on standard 12-core biopsy 6 months following HIFU therapy; rate of high grade cancer in the untreated lobe.

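### The 6-month negative biopsy rate after HIFU is stated differently in sections 3.1, 3.3 and 6.1, and 3.3 and 6.1 leave out targeted cores in the treated zone

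*Combined protocol and SAP*

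**What the plan says.** The 6-month sampling is set under HIFU Therapy and Follow Up Schedule: "MR/US-guided biopsy of all positive sites + systematic 12-core prostate biopsy at 6 months (or as clinically indicated". The HIFU calendar in 3.4.2 also lists a fusion-targeted biopsy beside the sextant biopsy at the post-treatment visit, with a window of 1.5 months either side of 6 months.

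The endpoint that uses these cores is worded as follows:

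- Study Summary: "Negative biopsy rate of standard 12-core biopsy 6 months following HIFU therapy". Section 3.3: "Negative biopsy rate on standard 12-core biopsy 6 months following HIFU therapy". Both name the 12-core biopsy and no region.
- Section 6.1: "Negative biopsy rate within treatment zones on standard 12-core biopsy 6 months following HIFU therapy; rate of high grade cancer in the untreated lobe". Still 12-core only, now limited to the treated zone, with a second outcome for the untreated lobe.
- Section 3.1: "prostate biopsy (MR/US-fusion biopsy plus standard sextant biopsy) to assess the negative biopsy rate in the treated region". Targeted cores are included. The sentence then adds freedom from Gleason grade 4/5 cancer in the untreated region and speaks of one secondary endpoint, in the singular.
- Section 1.0: "negative biopsy rate in the treated region and absence of Gleason grade 4 or 5 in the untreated region as secondary endpoints". The regions match 3.1, the plural is used, and no biopsy method is named.

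Two other rules bear on the point. Section 3.4.1 says: "Patients with low Gleason grade cancer (e.g. Gleason grade 3) on the contralateral lobe are allowed". Under Eligibility for HIFU, men with high grade disease in both lobes are kept out of this analysis: "Their data will be used to assess the primary endpoint but they will not be considered for secondary endpoints". No target rate, test or sample size is given for the endpoint.

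**The concern.** The statements differ on two axes: which tissue counts (whole gland or treated zone) and which cores count (systematic only, or systematic plus targeted). No section says which statement takes precedence.

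Three consequences follow from the wording:

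1. Read literally, 3.3 can score a man as a failure for low grade cancer that the protocol allowed to be left alone.
2. Under 3.3 and 6.1, cancer remaining in ablated tissue and found only by a targeted core does not count, although those cores are a required part of the visit.
3. Section 6.1 speaks of the untreated *lobe*, whereas 1.0 and 3.1 speak of the untreated *region*. After focal HIFU these are different tissue.

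This is the only post-treatment cancer outcome among the HIFU arm's primary and secondary endpoints. Analysts following different sections could report different rates from the same men, and the choice could be made once results are known.

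**Working it through.** The plan gives no figure for this endpoint, so there is none to reproduce. The check sets the definitions side by side, then works out what can be said about size.

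**Step 1. Classify the same man under each statement.** Here *sextant* in 3.1 is taken to mean the 12-core template.

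| Findings at 6 months | 3.3, literal | 6.1, zone rate | 3.1, treated region |
|---|---|---|---|
| A. Zone clear on all cores; Gleason grade 3 on a systematic core in the other lobe | positive | negative | negative |
| B. Only positive core is a targeted core in the zone | negative | negative | positive |
| C. Targeted core positive in the zone, systematic cores in the zone clear, and a systematic core positive outside it | positive | negative | positive |
| D. Focal HIFU; zone clear; Gleason grade 4/5 on a systematic core in the treated lobe outside the zone | positive | negative, and absent from the untreated-lobe outcome | negative, but counted in the untreated-region outcome |

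If 3.3 is read as short for 6.1, its column becomes the 6.1 column. Rows A and C then no longer separate 3.3 from 6.1. Row B still separates both from 3.1, and row D is still lost from both 6.1 outcomes.

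**Step 2. Order the rates.** Let T be the men treated. Among men with no positive systematic core in the zone, let:

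- a = no other positive core;
- x = positive systematic core outside the zone, zone clear on targeted cores;
- y = positive targeted core in the zone, nothing positive outside;
- w = both (row C).

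Then:

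- 6.1 = (a + x + y + w)/T
- 3.1 = (a + x)/T
- 3.3, literal = (a + y)/T
- 6.1 − 3.1 = (y + w)/T, never below zero
- 6.1 − 3.3 = (x + w)/T, never below zero
- 3.3 − 3.1 = (y − x)/T, either sign

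If 3.1 is a composite that also requires no Gleason grade 4/5 cancer in the untreated region, its rate can only fall further, so 6.1 still cannot be the lower of the two. If *sextant* means six cores, 3.1 no longer contains every core used by 6.1 and the order of those two is not guaranteed.

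**Step 3. Size per man.** The planned HIFU cohort is 30 (Study Summary, 6.1). The number actually treated is not stated and is at most about 30. One reclassified man moves the rate by:

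- 1/30 = 3.3 points at 30 treated
- 1/20 = 5.0 points at 20
- 1/10 = 10.0 points at 10

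**Step 4. One illustration, all counts assumed.** Take T = 30, a = 24, x = 3, y = 1, w = 0:

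- 3.1 = 27/30 = 90.0%
- 6.1 = 28/30 = 93.3%
- 3.3, literal = 25/30 = 83.3%

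The documents give none of x, y or w, so this shows the mechanism and is not an estimate.

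**The case against.** The best reply is that 6.1 is simply the full form of 3.3. Three of the five statements (1.0, 3.1 and 6.1) limit the rate to treated tissue. Section 6.1 is the statistical section and nearly repeats the 3.3 line with the zone added. That is the more natural reading, and it removes row A. It does not touch row B or row D.

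A reader might go further and infer that deliberately untreated cancer will nearly always be present, because the Gleason 6 entry route needs at least half of the systematic cores positive. The documents do not support that. HIFU on study requires unilateral high grade disease at the mapping biopsy, with clinician judgment on suitability, so a Gleason 6 entrant reaches this endpoint only if upgraded. Cancer seen at entry also need not be sampled again at 6 months. Section 3.4.1 supports *can count*, and no more.

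A fixed 12-core template is a legitimate and uniform read-out. That stands, and is why the 12-core zone rate should be kept as a supportive figure. But 3.1 commits to targeted cores, so the plan has to choose.

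Row D arises only with focal treatment, and the focal share is not stated. That also stands.

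Finally, with so few men the rate is imprecise anyway: 27/30 has an exact 95% interval of 73.5% to 97.9%. That is much wider than a shift of one to three men. But the shift is not sampling error; it is a different answer from the same biopsies.

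**Conclusion.** The inconsistency is real, and no section resolves it. On any reading of 3.3, two defects remain: 3.3 and 6.1 ignore targeted cores in the treated zone, and 6.1's *lobe* wording drops Gleason grade 4/5 cancer in the treated lobe outside a focal zone. Section 2.8 notes that true focal therapy ablates only identified lesions, so missed disease of this kind is what better mapping is meant to prevent. The failure of 3.3 to exclude untreated low grade cancer holds only on the literal reading.

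The size is unknown. It is at least about 3.3 points per reclassified man with at most about 30 treated. If *sextant* means the 12-core template, 6.1 gives a treated-zone rate at least as high as 3.1's. A reader might take that direction as certain, but without that assumption it is not. Nor can the 89% quoted in 2.3 be used to size the gap, since it names no region.

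The endpoint is secondary, with no test and no sizing. The primary endpoint and its power are unaffected. The change should be made, but this is a matter of one secondary definition and not a threat to the trial's main result.

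**What to change.** Use one definition in the Study Summary and sections 1.0, 3.1, 3.3 and 6.1:

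- **Population:** men treated with HIFU. The Eligibility for HIFU section already leaves out men with high grade disease in both lobes.
- **Negative:** no cancer on any systematic or targeted core within the treated zone at the 6-month biopsy (window of 1.5 months either side).
- **Supportive figure:** the rate in the same zone from the 12-core biopsy alone.
- **Separate outcome:** Gleason grade 4/5 cancer in the untreated region, replacing the untreated lobe in 6.1 and added to 3.3. State that it is not combined with the negative rate.
- **Descriptive listing:** Gleason grade 3 cancer outside the zone, not counted as failure.
- **Data:** record each core's type (systematic or targeted) and zone (treated or not) when the biopsy is taken. Show treated men without a 6-month biopsy as a separate count.

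The cost is wording in five places, a few case report form fields, and an amendment with IRB approval under 7.4.5. No biopsy or visit is added, because both core types are already planned. The headline rate may be slightly lower than the 12-core zone rate, which is the reason to show both.

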## 3.5 Removal of Subjects from study

Patients can be taken off the study at any time at their own request, or they may be withdrawn at the discretion of the investigator for safety, behavioral or administrative reasons. The reason(s) for discontinuation will be documented and may include:

- **3.5.1** Patient voluntarily withdraws (follow-up permitted);
- **3.5.2** Patient withdraws consent (discontinue all study procedures and follow-up)
- **3.5.3** Patient is unable to comply with protocol requirements;
- **3.5.4** Treating physician determines continuation on the study would not be in the patient's best interest;
- **3.5.5** Lost to follow-up. If a research subject cannot be located in order to obtaining data to inform the primary or secondary endpoint, the subject may be considered "lost to follow-up." All attempts to contact the subject during the two years must be documented.

# 4.0 Study Risks

This study investigates a novel software-based MRI imaging protocol that improves image resolution, and it investigates the use of F18-PSMA for prostate PET-MRI.

F18-PSMA is currently not approved by FDA. MR/ultrasound fusion biopsies and HIFU for prostate ablation are approved procedures that are being routine performed as standard-of-care. All invasive procedures will therefore be performed following standard informed consent.

